2.5 NIH PHASE I BMSC TRIAL (12-H-0010)

2.5.1 NIH Phase I Clinical Trial Design

Results from the Phase I trial of BMSC at NIH were recently published³⁹ and reviewed⁸³. At the NIH Clinical Center, we developed a clinical grade BMSC cell bank from third party donors^{37,38}. We approached the development of BMSC by selecting the EU method of using early passage BMSC. The infusion schedule of doses of 2x10⁶ BMSC/kg weekly followed previously used schedules effective for controlling GVHD⁸⁴. We conducted the phase I trial using our third party, early passage BMSC for patients with steroid-resistant liver or gastrointestinal GVHD, tissue injury or marrow failure following allogeneic stem cell transplant. The study schema is depicted in Figure 1.

The BMSC were prepared from marrow aspirates from healthy volunteers with the expansion of 3 passages³⁸. Ten subjects were infused a fixed dose of 2e10⁶ BMSC/kg intravenously weekly for three doses. Nine of the subjects had acute GVHD as the primary indication. There was no treatment related toxicity (primary endpoint). In addition to the demonstration of safety and exploration of efficacy, the major objective was to understand the biology of BMSC in post-transplant complications. The infused

Abbreviated Title: Early BMSC Pilot for Acute GVHD

Version Date: 6/16/2016

BMSC were fully characterized in terms of viability, freeze-thaw characteristics, and gene expression profiles with the goal of identifying markers for potency. We examined the impact of BMSC in terms of their immunogenicity by HLA-alloimmunization, their homing, and fate (by chimerism analysis). Advances in new diagnostic tools using GVHD-relevant biomarkers and markers of tissue injury provided the opportunity to more clearly define responses to BMSC⁸⁵. Patients were monitored for validated plasma GVHD biomarkers, cytokines, growth factors, and lymphocyte phenotype before and after BMSC infusion to identify mechanisms of BMSC immunomodulation and tissue repair.

2.6 SAFETY OF BMSC INFUSIONS

Safety is a significant concern when translating any new therapeutic into clinical practice. Issues specific to BMSC therapy include the risk of infusion toxicity; an increased susceptibility to infection given their immune-modulatory effects; the dissemination of zoonoses associated with cell culture reagents; an increased neoplastic potential due to the proliferative capacity of BMSC; the potential for embolism of cells; and, the immunogenicity of the cells themselves⁸⁶. BMSC have been used safely in clinical practice for over 10 years; neither acute nor long-term adverse events have been reported after infusion of autologous, donor-derived, or third party BMSC⁸³. Safety of intravascular BMSC infusions in humans was reviewed systematically in October, 2012⁵³. In a meta-analysis of 36 studies that were deemed eligible, including eight RCTs, the authors were unable to detect an association between BMSC treatment and infusion toxicity, infection, malignancy, acute organ dysfunction, and death. In fact, six of seven RCTs and all non-RCTs described equal or fewer deaths with BMSC treatment compared to control treatment. The only significant association with BMSC treatment was transient fever. Our

Abbreviated Title: Early BMSC Pilot for Acute GVHD

Version Date: 6/16/2016

chosen dosing schedule of 2×10^6 cells/kg/dose twice weekly for four weeks with additional dosing for partial responders is more treatment than in many earlier trials of early passage BMSC, but this same regimen has been shown to be safe and effective in studies using Prochymal®, the universal donor, late passage BMSC product and another similar BMSC product that is being developed in Japan^{75,81}.

2.6.1 Safety of the NIH BMSC Product

The phase I study met the primary objective of safety³⁹. Protocol defined treatment-related SAE was encountered by none of the subjects. Infusion reactions were seen in one subject (grade 1 pruritus). There was one death while on study (gram-negative bacterial sepsis). There were seven serious adverse events: bacterial infection (n=5), gastrointestinal bleeding (n=1), and a mucus plug in the respiratory tract (n=1). In addition, there were 13 non-SAEs: grade 1 (n=7), grade 2 (n=4), and grade 3 or 4 (n=2). None of these adverse events were attributable to the BMSC product. The HLA antibody screen remained negative prior to and immediately after completing the BMSC trial. New CMV reactivation without the development of CMV organ diseases occurred in two patients, controlled by pre-emptive antiviral therapy.

2.6.2 Safety in Pediatric Patients

Several studies have shown significant clinical benefit of BMSC for refractory acute GVHD in the pediatric setting, which are at least comparable to their adult counterparts, and there have been no reports of serious adverse events attributable to BMSC infusion (see Section 3.8.4). Published pediatric studies with BMSCs with doses as high as 8×10^6 cells per kilogram body weight have demonstrated safety and efficacy for steroid refractory GVHD and to enhance engraftment^{43,63,67,81,87}. A pre-manufactured, universal donor formulation of BMSC (Prochymal®) has been approved as the first stem cell product for refractory acute GVHD in children in Canada and New Zealand⁸⁸.

2.7 SCIENTIFIC AND CLINICAL JUSTIFICATION

The scientific rationale for expanding the use of BMSC to the initial treatment of GVHD is based on preliminary efficacy in the settings of both GVHD prophylaxis and refractory GVHD, the known properties of BMSC to assist in tissue repair and suppress alloimmune responses causing GVHD, and a track record of safety in human subjects. Importantly, treatment with BMSC offers an opportunity to study changes in GVHD biomarkers in the blood before and after BMSC infusion and before, during, and after the onset of GVHD. One of the major obstacles in GVHD research is that GVHD is a heterogeneous illness and responses to therapy can vary widely from study to study and BMSC preparation to BMSC preparation. One of the keys to understanding responses in GVHD may be the discovery of ST2 as a predictive biomarker of GVHD severity and subsequent mortality related to GVHD⁸⁹. Plasma collected at regular intervals after BMSC infusion will be used to study changes in these cytokines. It has been shown recently that BMSC recipients have increased serum CD73-expressing BMSC exosomes in the blood (submitted for publication), and BMSC exosomes are immunologically active⁹⁰.

2.8 RATIONALE FOR CHANGES FROM PHASE I STUDY

The previous phase I study used a dosing schedule of 2×10^6 BMSC/kg once weekly for three weeks in refractory GVHD, whereas the proposed pilot study will use a dosing schedule of 2×10^6 BMSC/kg twice weekly for four weeks for early GVHD, followed by once weekly for 4 weeks in patients who have a suboptimal response. Below is justification for the change in schedule.

Abbreviated Title: Early BMSC Pilot for Acute GVHD

Version Date: 6/16/2016

2.8.1 Upfront treatment

Acute GVHD is caused by a cascade of events that ultimately lead to alloreactivity and tissue damage. Mechanistically, reversing the processes underlying GVHD early may break the cycle of alternating tissue damage and immune activation, thereby preventing progression to refractory GVHD. In a pediatric study by Ball *et al.*⁷⁷, of 37 children, those treated with BMSC between 5 and 12 days after steroid initiation showed a trend towards better OS (56%) and lower TRM (17%) as compared with patients receiving BMSC 13–85 days after initiation of steroids (25% and 53%, respectively; P = 0.22 and 0.06, respectively). More recent studies have prioritized early treatment with BMSC in refractory GVHD^{75,79,81} (see Table 2).

2.8.2 Increased number and frequency of doses

Also in the study by Ball *et al.* cited above⁷⁷, the authors retrospectively analyze their results in a series of 37 children with steroid-resistant acute GVHD. Multiple doses of BMSC were associated with a higher rate of CR. Cumulative incidence of transplantation-related mortality (TRM) in patients who did or did not achieve CR was 17% and 69%, respectively. In a more recent manuscript describing the Spanish experience, investigators examined a dosing schedule of 1×10^6 BMSC/kg on days 1, 4, 11, and 18 for treatment refractory acute GVHD and found an ORR of 71%. Most patients received 3 or more infusions, and additional infusions were allowed in patients achieving a partial response. A maximum of 8 infusions were given in two patients and proved to be safe⁷⁹. In a larger study⁸¹, Kurtzberg *et al.* reported on 75 children with treatment-resistant grade II - IV acute GVHD who received the pre-manufactured, universal donor formulation of BMSC (Prochymal®). The BMSC dose was 2×10^6 cells/kg/dose infused twice weekly for 4 weeks. In the case of a partial or mixed response, patients were treated with 2×10^6 cells/kg/dose weekly for four more weeks. This is the same schedule proposed in our study. Patients received a median of 10 doses. At the start of treatment, the majority of patients had grade III (28.0%) or grade IV (60.0%) refractory acute GVHD and patients were heavily pretreated with immunosuppression. The overall response rate was 61.3% at day 28. No infusion or other identifiable acute toxicity was seen in any patient.

2.8.3 Continuation of therapy

In the pediatric study previously cited by Kurtzberg *et al.*⁸¹, in the case of a partial or mixed response after 2×10^6 cells/kg/dose twice weekly for 4 weeks, patients were treated with 2×10^6 cells/kg/dose weekly for an additional four weeks and assessed again for response. For a patient to be considered a responder between day 28 and day 100, they must have experienced additional improvement in at least 1 organ of at least 1 stage without worsening in any other organ. Forty (40) patients on this study received more than the planned 8 infusions and more than one-half of these patients (57.5%) demonstrated additional improvement in acute GVHD, with 16 patients achieving complete resolution of acute GVHD.

2.8.4 Addition of pediatric patients

Several studies have shown significant clinical benefit of BMSC for acute GVHD in the pediatric setting, which are at least comparable to their adult counterparts. In the largest cohort of children to date^{68,81}, Kurtzberg *et al.* reported on 75 children with treatment-resistant grade II - IV acute GVHD who received Prochymal®. The BMSC dose was 2×10^6 cells/kg/dose, and infused twice weekly for 4 weeks. In the case of a partial or mixed response, patients were treated with 2×10^6 cells/kg/dose weekly for four more weeks. Patients received a median of 10 doses. At the start of treatment, the majority of

Abbreviated Title: Early BMSC Pilot for Acute GVHD**Version Date: 6/16/2016**

patients (88%) had grade III (28.0%) or grade IV (60.0%) acute GVHD. Many patients (60%) had received two or more immunosuppressive therapies in addition to steroids. The overall response rate was 61.3% at day 28. No infusion or other identifiable acute toxicity was seen in any patient. Prochymal® is approved for use in Canada and New Zealand for refractory GVHD in pediatric patients. Similar results have recently been reported in a smaller European pediatric study of eleven (11) patients with acute or chronic GVHD (grade I to IV) who received HLA-disparate donor's bone marrow-derived BMSC, expanded in platelet-lysate containing medium on compassionate use studies⁶⁷. The median dose administered to patients (aged 4-15 years) was 1.2×10^6 cells/kg/dose (range: $0.7-3.7 \times 10^6$ cells/kg/dose). No acute or late side effects were reported with a median follow up of 8 months. The overall response rate was 71.4% (CR = 23.8%). Müller *et al.* reported on the administration of ex vivo-expanded BMSC in seven pediatric patients in escalating doses (0.4×10^6 to 3.0×10^6 cells/kg/dose)⁶³. No adverse effects were observed in a follow up of 29 months.

3. STUDY DESIGN**3.1 STUDY DESIGN**

This is a pilot trial designed to explore the feasibility of using BMSC combined with standard therapy for the initial treatment of acute GVHD requiring systemic therapy

3.1.1 Accrual Objective

Twenty-five (25) patients will be accrued with the goal of attaining twenty-three (23) evaluable patients.

3.1.2 Accrual Period

The estimated accrual period is 18 months.

3.1.3 Study Duration

The expected maximum duration of treatment according to the study protocol will be 11 weeks total as outlined in Section 3.4.

3.1.4 Rationale for Design

Twenty five patients over 12-18 months is a realistic target for accrual given the incidence of acute GVHD in the clinical center.

3.2 SUBJECT INCLUSION

Provided subjects satisfy inclusion criteria in Section 5.1, the protocol is open to all subjects transplanted at NIH who are diagnosed with acute GVHD, irrespective of conditioning regimen, primary disease, or transplant type. The protocol will include subjects at any time after allogeneic stem cell transplantation.

3.3 INITIAL ASSESSMENT

Subjects will be assessed by clinical laboratory criteria and also where appropriate, by biopsy for degree and severity of GVHD of the liver and/or gastrointestinal tract according to criteria in Appendix 1. Patients with confirmed acute GVHD will be enrolled within 120 hours of receiving systemic corticosteroids for the treatment of acute GVHD.

Abbreviated Title: Early BMSC Pilot for Acute GVHD

Version Date: 6/16/2016

3.4 TREATMENT

3.4.1 Schema and Treatment Summary

[figure not shown]

Figure 3 - Study schema

This is a pilot trial where eligible subjects may be entered into this study if they meet the diagnostic criteria for acute GVHD requiring systemic corticosteroid therapy. Subjects will receive the first infusion of BMSC within 120 hours of the first dose of systemic corticosteroids. Each subject will receive 2×10^6 cells/kg of BMSC given twice weekly, no sooner than 48 hours apart, for 8 doses. Four (4) additional weekly doses will be given in the absence of a complete response. BMSC will be given for a maximum of 12 doses. We will endeavor to administer BMSC on Tuesdays and Fridays in order to facilitate planning with CPS DTM. Each BMSC infusion will contain a target dose of 2×10^6 BMSC/kg ($\pm 10\%$) viable BMSC (30-150 mL). Donor sample identifiers will be tracked for each infusion. Since there are no specific or antidotal therapies for AEs arising from BMSC, any toxicity that arises during the subject's infusion or post infusion assessments will be managed with standard supportive care as outlined below. Patients will also be treated with systemic corticosteroids per established treatment guidelines (Section 3.4.3).

3.4.2 Treatment with BMSCs

3.4.2.1 Pre-infusion

Pre-infusion steps will be followed according to the NIH institutional standard operating procedure: [Administration of Products of Cellular Therapy](#). Emergency equipment will be made available in the patient room including: oxygen, suction machine, vital signs monitor, and 0.9% sodium chloride solution and administration. All adult subjects will receive diphenhydramine 25-50 mg IV or PO over 10-15 minutes and/or acetaminophen 325-650 mg PO 30-60 minutes prior to infusion; all pediatric subjects will receive diphenhydramine 0.5-1 mg/kg IV or PO over 10-15 minutes (max dose 50 mg) and/or acetaminophen 10-15 mg/kg PO (max dose 650 mg) 30-60 minutes prior to infusion. Subjects will remain in the NIH Clinical Center (inpatient ward or day hospital) to be evaluated for toxicity as specified by the standard operating procedure. Pre-medications may be substituted. Acetaminophen can be held for patients with abnormal liver function studies.

3.4.2.2 Infusion

BMSC infusions will be scheduled with the CPS DTM in advance. BMSC will be thawed rapidly in a 37°C water bath. BMSC bags will be hand carried by CPS personnel to the patient care unit. BMSC will be administered according to NIH institutional standard operating procedure: [Administration of Products of Cellular Therapy](#). In brief, subjects will be present either in the inpatient ward or the day hospital during the entire time of the infusion. It is recommended to use a central venous catheter for infusion of BMSC, but a patent peripheral access is acceptable. Infusion rate shall not exceed 4-5 mL/min (approximately 10-30 minutes) by gravity. The product should not be given by an infusion

Abbreviated Title: Early BMSC Pilot for Acute GVHD**Version Date: 6/16/2016**

pump. The total dose of the product given with each infusion is 2×10^6 BMSC/ kg (+/- 10%) viable BMSC (30-150 mL).

3.4.2.3 Post-infusion

Patients will be monitored post-infusion according to the NIH institutional standard operating procedure: [Administration of Products of Cellular Therapy](#). Outpatients may be released thirty minutes to one hour after completion of infusion if patient condition and vital signs are stable, as specified in the standard operating procedure above.

3.4.2.4 Missed infusions

Unanticipated logistical challenges including, but not limited to, adverse weather, availability of transportation, or equipment-related delays may occur. Subjects can miss up to four (4) BMSC infusions in total over the course of the treatment protocol and remain enrolled and evaluable for response. If an infusion or series of infusions are missed, the infusion will not be rescheduled and the subject will go on to receive the next scheduled infusion in the treatment course. Subjects missing more than four (>4) BMSC infusions will be removed from the treatment protocol and will not be evaluable for the primary endpoint.

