The Cell Processing Section of the Department of Transfusion Medicine at the Clinical Center NIH has developed a BMSC repository at NIH. The NIH BMSC are a third party, early passage product based on the EU manufacturing approach. The NIH BMSC cellular product was administered safely to transplant recipients with steroid-resistant acute GVHD in a phase I study (protocol 12-H-0010, IND #14596) conducted from March 2012 to October 2012 at NIH. This pilot study is a continuation of the previous study and open to allogeneic stem cell transplantation recipients at NIH (age ≥ 4 yrs) with *de novo* acute GVHD requiring systemic therapy, either directly after allogeneic transplantation or following treatment with donor lymphocyte infusion. Subjects will receive BMSC infusions (target dose of 2×10^6 BMSC/kg for up to 12 doses) in addition to standard upfront therapy with corticosteroids. The primary endpoint will be the proportion of patients without a treatment-related severe adverse event (TRSAE) at day +56. Responses will be assessed at day +28 and +56 from the initial diagnosis. Responses will be correlated to changes in GVHD biomarkers including ST2, Reg3a, TNFR1, and IL-6. Subjects will be enrolled at first diagnosis of acute GVHD, and the first BMSC infusion will be given within 120 hours of the first dose of corticosteroids. BMSC infusions will be given twice weekly for the first 4 weeks. Subjects with a complete response at the end of week 4 will not receive further infusions. All other subjects will receive BMSC infusions weekly for four additional weeks. Safety will be monitored continuously with a stopping rule for toxicity based on the treatment-related serious adverse event rate. Research samples will be drawn at regular intervals to explore biological correlates of response and to investigate the mechanism of action of BMSC.

Abbreviated Title: Early BMSC Pilot for Acute GVHD

Version Date: 6/16/2016

TABLE OF CONTENTS

1. INTRODUCTION	5
1.1 Study Objectives	5
2. BACKGROUND	5
2.1 Acute Graft-versus-Host Disease	5
2.2 Primary Therapy for Acute GVHD	6
2.3 Biology of Bone marrow-derived mesenchymal stem cells.....	6
2.4 Clinical Experience With BMSC in GVHD	7
2.5 NIH Phase I BMSC Trial (12-H-0010).....	10
2.6 Safety Of BMSC Infusions	11
2.7 Scientific And Clinical Justification	12
2.8 Rationale for Changes from Phase I Study	12
3. STUDY DESIGN.....	14
3.1 Study Design	14
3.2 Subject Inclusion	14
3.3 Initial Assessment	14
3.4 Treatment	15

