11. BIOSTATISTICAL CONSIDERATIONS

11.1 PRIMARY ENDPOINT

The primary endpoint of this study is:

- The proportion of subjects reaching day +56 without a TRSAE.

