11.3.2 Sample Size

Let p be the probability of subjects reaching day +56 without a TRSAE. The sample size is determined by testing the null hypothesis $H_0 : p = 75\%$ versus the alternative hypothesis $H_a : p > 75\%$ with a one-sided significant level of 0.05. Based upon our previous phase 1 trial (12-H-0010), the TRSAE rate was 0 out of 10 subjects and we expect 95% subjects would reach day +56 without a TRSAE. Thus a sample size of 23 subjects will achieve 89.5% power to test the above hypotheses using an exact binomial test.

To account for the possibility of non-treatment related drop out, up to 2 additional subjects may be enrolled to replace those subjects that are non-evaluable for the study's primary endpoint for a total accrual of 25 patients. At an accrual rate of 1-2 subjects per month, this study will be completed in 12-18 months.

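### One missed-infusion limit covers both the 8- and the 12-infusion course, so evaluability for the primary safety endpoint depends on day +28 response

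*Combined protocol and SAP*

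**What the plan says.** **Limit.** Section 3.4.2.4: "Subjects can miss up to four (4) BMSC infusions in total over the course of the treatment protocol". Beyond that, "Subjects missing more than four (>4) BMSC infusions will be removed from the treatment protocol and will not be evaluable for the primary endpoint".

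**Course length.** Section 3.4.1 plans infusions "given twice weekly, no sooner than 48 hours apart, for 8 doses" for every subject, and then "Four (4) additional weekly doses will be given in the absence of a complete response". The protocol's opening summary agrees: "Subjects with a complete response at the end of week 4 will not receive further infusions". The course is 8 infusions with CR and 12 without.

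**Primary endpoint.** Section 11.1: "The proportion of subjects reaching day +56 without a TRSAE".

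**Allowance and replacement.** Section 11.3.2 needs 23 evaluable subjects and allows up to 2 more to replace non-evaluable ones. Section 11.3.3 has a different rule: subjects with fewer than two completed doses are replaced.

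**Response.** Section 3.4.2.4 says subjects within the limit stay evaluable "in total over the course of the treatment protocol and remain enrolled and evaluable for response". Section 11.2 takes the response proportions over patients alive at day +28 and day +56, with no missed-infusion condition.

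**The concern.** A single absolute limit is applied to two course lengths, and the course length is itself an outcome. A subject in CR at week 4 has no further infusions to miss. A subject without CR has four more chances to cross the limit. Whether a treated subject counts in the primary analysis therefore depends partly on day +28 response.

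For a safety endpoint this is hard to justify. Subjects who cross the limit in weeks 5-8 have been treated and observed for at least four weeks, and they belong to the group with the longer planned exposure. Section 3.4.2.4 explains missed infusions by logistics and gives no scientific reason for discarding safety data. At stake are a cleanly defined primary analysis set and, if many infusions are missed, the 23 evaluable subjects that the power rests on.

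**Working it through.** **Inputs.** Limit: more than 4 missed (Section 3.4.2.4). Planned infusions: 8, or 8 + 4 = 12 (Section 3.4.1). Test: null 0.75, alternative 0.95, one-sided 0.05, 23 evaluable plus up to 2 (Section 11.3.2); rejection at 21 or more of 23 (Section 11.3.4.2). The plan assumes no CR rate; the trials it cites report day +28 CR of 26% to 60% (Section 2.2.1) and 71% (Section 2.4.2). The miss probability q is not given. It is assumed here to be independent across infusions and equal in both groups, at 0.1, 0.2 and 0.3.

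**1. The plan's own figure.** P(X ≥ 21 | 23, 0.75) = 0.0492 and P(X ≥ 21 | 23, 0.95) = 0.8948. The stated 89.5% power reproduces.

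**2. Tolerance.** 4/8 = 50% against 4/12 = 33%. A subject in CR is evaluable after 4 infusions. A subject who crosses the limit in weeks 5-8 missed at most 4 of the first 8, so received at least 4 and at most 12 − 5 = 7. That subject is dropped despite having had no fewer infusions than the least-treated evaluable CR subject.

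**3. Chance of being non-evaluable.** Let a = P(Bin(8,q) ≥ 5), b = P(Bin(12,q) ≥ 5) and c = the CR rate. Extra removals due to the four added infusions are 25(1−c)(b−a). Total non-evaluable is 25[ca + (1−c)b].

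| q | a (CR) | b (no CR) | Extra of 25, c = 71% to 26% | Total of 25, c = 50% |
|---|---|---|---|---|
| 0.1 | 0.04% | 0.4% | 0.03 to 0.07 | 0.06 |
| 0.2 | 1.0% | 7.3% | 0.45 to 1.15 | 1.0 |
| 0.3 | 5.8% | 27.6% | 1.6 to 4.0 | 4.2 |

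For example, at q = 0.2 the total is 25 × 0.5 × (0.0104 + 0.0726) = 1.04.

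**4. Sample size.** The allowance is 2. If evaluable N falls to 22, the smallest cutoff with level at most 0.05 is 21/22, with power 69.8%. At 21 it is 20/21, with power 71.7%.

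**5. Primary estimate.** The CR share among evaluable subjects is w = c(1−a)/[c(1−a) + (1−c)(1−b)]. With c = 50%, w is 50.1%, 51.6% and 56.6% at q = 0.1, 0.2 and 0.3. If misses are unrelated to TRSAE within each response group, the expected TRSAE-free proportion shifts by (w − c) times the difference in TRSAE-free probability between groups. Each percentage point of difference moves the estimate by 0.016 points at q = 0.2 and 0.066 points at q = 0.3. The documents give neither the sign nor the size of that difference.

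**6. Infusions withheld after a TRSAE.** Sections 8.3 and 9.1.1 stop infusions after a TRSAE. Section 3.4.2.4 does not say whether the withheld ones count as missed. If they did, and nothing had been missed before, a TRSAE after infusion 3 or earlier of 8 (8 − 3 = 5), or after infusion 7 or earlier of 12 (12 − 7 = 5), would make the subject non-evaluable for the endpoint that counts TRSAEs.

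**The case against.** The case against is substantial on consequence.

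- **Selective removal of non-responders.** A reader might infer this, but the documents do not support it. Nobody is removed for not responding. The 12-infusion group is everyone without CR, partial responders included. Removal takes at least five misses, and a CR subject who misses 5 of 8 is removed too. What stands is an unequal chance of crossing the limit.
- **Response rates biased upward.** The sentence that removes evaluability names only the primary endpoint. Section 11.2 uses surviving patients as the response denominator, and Sections 3.6 and 6.2.1 record response at both days without a missed-infusion condition. Losing a recorded day +28 response is one reading of an ambiguous sentence. Even on that reading, a true 50% CR rate would appear as 51.6% at q = 0.2, against a standard error of √(0.25/23), about 10 points.
- **TRSAE-free proportion biased favourably.** This needs TRSAE risk to differ by response. No such data are given; the phase 1 trial had 0 TRSAEs in 10 subjects. The stopping rule in Section 11.3.4.2 counts any subject with a TRSAE, evaluable or not.
- **Sicker subjects miss more.** The documents do not say so. The causes named are weather, transport and equipment, and Section 13.1.2 expects almost all subjects to be in hospital. Transport problems could fall on well outpatients instead.
- **Miss rates.** They are assumed. At q = 0.3, with 50% CR, 4.2 of 25 subjects would be non-evaluable, about twice what the plan allows for.

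These points limit the size of the effect. They do not explain why evaluability for a safety endpoint should depend on course length, and therefore on response.

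**Conclusion.** The defect is real and modest. Section 3.4.2.4, read with Section 3.4.1, makes evaluability for the primary safety endpoint depend on day +28 response and drops treated subjects who may have had more infusions than an evaluable CR subject. With equal, independent misses the effect is negligible at q ≤ 0.1 and begins to matter at about q = 0.2. By q = 0.3 expected losses exceed the allowance of 2, and power would fall with the evaluable number. All of this rests on assumed miss rates.

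The documents do not establish bias in the TRSAE-free proportion in either direction. Whether response results are also lost is ambiguous between Sections 3.4.2.4 and 11.2. The silence on infusions withheld after a TRSAE is a related gap that bears more directly on the primary endpoint.

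**What to change.** Separate analysis evaluability from the missed-infusion rule. No dosing or treatment rule needs to change.

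1. In Section 3.4.2.4, remove the loss of evaluability. Keep treated subjects in the primary safety analysis whatever infusions they miss later.
2. State that infusions withheld after a TRSAE are not missed infusions, and that any subject with a TRSAE counts as an event, including one who is removed or replaced.
3. Keep every recorded day +28 and day +56 response, consistent with Section 11.2.
4. Report infusions received over infusions planned (8 or 12) for each subject.
5. Base any supportive adherent subset on misses among the first 8 infusions, which all subjects share.
6. Reconcile Sections 3.4.2.4, 11.2, 11.3.2 and 11.3.3 into one defined analysis set, saying how subjects below two doses are handled.

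The cost is wording. The test on 23 subjects is unchanged, and the Appendix 3 calendar already lists adverse-event collection through day 56. The downside is that the primary analysis will include under-dosed subjects, so the adherent-subset result should be shown beside it.
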